6.4.2 Recipient Exclusion Criteria

Subjects will be excluded from the study if one of the following conditions is present:

1. Diagnosis of co-existing cardiac disease, characterized by any one of these conditions:
 - a. Recent myocardial infarction (within past six months), or
 - b. Angiographic evidence of non-correctable coronary artery disease, or
 - c. Evidence of ischemia on functional cardiac exam (with a stress echo test recommended for subjects with a history of ischemic disease).
 - d. Heart failure > New York Heart Association II
2. Active alcohol or substance abuse includes cigarette smoking (must be abstinent for six months). Active alcohol abuse should be considered using the current National Institute on Alcohol Abuse and Alcoholism definitions.
3. Psychiatric disorder making the subject not a suitable candidate for transplantation, e.g., schizophrenia, bipolar disorder, or major depression that is unstable or uncontrolled on current medication. (A psychological or psychiatric consultation is required only if considered necessary by some current indication or history.)
4. History of non-adherence to prescribed regimens
5. Active infection including hepatitis C, hepatitis B, HIV
6. TB (by history or currently infected as evidenced by a positive QuantiFERON® - TB Gold test or under treatment for suspected TB)
7. Any history of malignancies except squamous or basal skin cancer. Any subject found to have squamous or basal cancer is required to have it removed prior to transplant.

8. Known family history of MEN2 or MCT
9. History of stroke within the past 6 months
10. BMI > 27 kg/m²
11. C-peptide response to glucagon stimulation (1 mg iv) (any C-peptide ≥ 0.3 ng/mL)
12. Inability to provide informed consent
13. Age less than 18 or greater than 75 years
14. Creatinine clearance < 80 mL/min/1.73 m² by 24-hour urine collection. If corrected creatinine clearance is < 80 and serum creatinine is < 1.2 mg/dL, then a nuclear renal scan is required to determine glomerular filtration rate.
15. Serum creatinine consistently > 1.5 mg/dL
16. Macroalbuminuria (urinary albumin excretion rate > 300 mg/24h)
17. Baseline Hb < 12 gm/dL in women or < 13 gm/dL in men

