6.6.7 Post-Transplant Period (see Appendix Detailed Visit Schedule)

Following transplant of islet cells, subjects will monitor their own glucose levels at home. Subjects will be asked to record results in a log for review at the next study visit. Blood samples for analysis (see Appendix *Detailed Visit Schedule*) are drawn three times per

week for the first two weeks and twice a week until the end of the 10th week (see Section 6.6.8 *Schedule of Evaluation*).

Subjects will come to the Clinical Research Center for visits and tests 3 times a week for the first two weeks, then twice per week for another 2 weeks, then weekly until week 12 after transplantation, then gradually tapered to every month during the first year. Additional visits may be necessary. The last study visit will be 52 weeks after transplantation. Additional evaluations may be required for medical conditions presenting during the study period and according to best medical practice.

When a second or third transplant is completed, the follow-up visit schedule is re-started to permit careful follow-up during the immediate post-operative period. In the event a second transplant is not needed due to successful engraftment, insulin independence, and stable blood glucose levels, the follow-up schedule will be maintained at monthly intervals following week 12 through the first year study period according to the *Schedule of Evaluation* in Section 6.6.8.

As in any other transplant situation, medical conditions that arise (e.g., new serious infection, malignancy, compliance issues, etc.) will automatically trigger a re-evaluation to determine if the subject remains qualified for continuous immunosuppression and subsequent transplants, if applicable.

The following laboratories will perform analyses of blood and urine samples:

CMV antibody panel, EBV antibody panel, C-peptide, insulin, anti-islet cell antibodies, anti-IA2, anti-GAD65, and anti-insulin antibodies will be analyzed at:

*ARUP Laboratories
[name]
[name]*

CMVqPCR and EBVqPCR will be analyzed at:

*ViraCor
[name]
[name]*

Inflammatory and detailed lipid panels will be analyzed at:

*CRL Medinet, Inc.
[name]
[name]*

Autologous crossmatch and donor crossmatch will be analyzed at:

*Gift of Hope Organ & Tissue Donor Network Histocompatibility Laboratory
[name]
[name]*

PRA and HLA will be analyzed at:

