University of Illinois at Chicago Tissue Typing Laboratory

[name]
[name]

All the other analyses will be performed at:
UIC Pathology Laboratory
[name]
[name].

The following exams and blood test will be performed according to the *Schedule of Evaluation* (see Section 6.6.8 and Appendix *Detailed Visit Schedule*):

- History, and adverse event and toxicity assessments (reviewed at each visit and recorded at any time necessary)
- Physical exam including vital signs (blood pressure, heart rate, respiratory rate, temperature)
- Body mass index (BMI: body weight in kilograms over square of height in centimeters)
- Electrocardiogram (ECG)
- Comprehensive metabolic profile (CMP):
 - Na⁺, K⁺, Cl⁻, Ca⁺⁺, CO₂, creatinine, BUN, glucose, total protein, albumin, total bilirubin, direct bilirubin, ALP, AST, ALT, alkaline phosphatase
- Complete blood count (CBC):
 - Hemoglobin, hematocrit, red blood cells, white blood cells, differential,, platelets
- Serum pregnancy test
- Urine analyses
 - Urinalysis
 - Creatinine, microalbumin, total protein
 - M/c ratio (microalbumin-creatinine ratio) 24-hour specimen at phase 1 screening, and random specimens thereafter unless a 24-hour specimen is medically indicated by elevated results from random sampling
- Drug levels
 - Tacrolimus and sirolimus trough levels to reach target levels defined in Section 6.5.2
- Cytomegalovirus (CMV) viral load by real time PCR
- Epstein-Barr virus (EBV) viral load by real time PCR
- HbA1c, basal C-peptide, fructosamine
- Blood sugar self monitoring (BS-SM)
- Metabolic tests to evaluate insulin-secretory capacity of the islet graft:
 - The following metabolic tests will be done on separate days. The tests are performed after an overnight fast greater than or equal to 10 hours; subjects may drink water. For subjects still on insulin injections, long-acting insulin may be taken no less than 8 hours prior to the test; no food or short-acting insulin may be taken within 5 hours of the test. Humalog should not be taken within 4 hours of the test. If a subject's blood glucose reading is 15 mM or greater (> 270 mg/dL) on the morning of the test, the test will be

rescheduled rather than to perform a procedure which will greatly increase the glucose levels. Additionally, subjects must have consumed at least 150 gm carbohydrate in their diet for the 3 days leading up to the test.

IVGGT, intravenous glucose tolerance test

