- An intravenous line is inserted on each arm, and 300 mg/kg of glucose (using a 50% glucose solution) is injected as rapidly as the subject tolerates and within less than 3 minutes. Blood samples for glucose, C-peptide, and insulin measurement are drawn at time -10, -1 (before injection), 2, 3, 4, 5, 6, 8, 10, 15, 20, 30, 40 minutes after glucose injection.
- The acute insulin response will be defined as the mean of the 3, 4 and 5 minutes insulin values with the mean of the basal values (-10 and 0 minute) subtracted.

○ GST, glucagon stimulation test

- Glucose, C-peptide, and insulin levels are measured before and six minutes after injecting a bolus of 1 mg of glucagon (Glucagen[®], Novo Nordisk Pharma SA) or the equivalent intravenously.

○ OGGT, oral glucose tolerance test

- Starting at time 0 the subject consumes a drink containing 75 gm of glucose (in 300 mL solution) over a 5-minute period. Blood samples for glucose, C-peptide, and insulin are drawn before and at 30, 60, 90 and 120 minutes after the subject begins the drink.

○ MMTT, mixed meal tolerance test

- A fasting blood sample for serum glucose, insulin, and C-peptide is drawn just before the test. At time 0, the subject is given Ensure High Protein[®] or Boost[®] to drink in the amount of 6 mL per kg body weight to a maximum of 360 mL, which is to be consumed within 5 minutes. Ninety minutes from time 0, another blood sample is drawn for serum glucose, insulin, and C-peptide.

- Detailed lipid panel
 - Total cholesterol, direct LDL cholesterol, HDL cholesterol, triglycerides, apolipoprotein B, apolipoprotein A1, free fatty acids, and lipid fraction ratio
- Lipid panel
 - Cholesterol, HDL, triglycerides, LDL cholesterol
- Inflammatory panel
 - CRP, MCP, MMP9, CAM, VCAM, fibrinogen, PAI-1 (antigen), TPA
- B-type natriuretic protein (BNP)
- ABO/RH (UNOS requires 2 independent blood type tests)
- Panel reactive antibodies (PRA)
- Antibodies: anti-GAD 65, anti-IA2, anti-islet cell, and anti-insulin
- IL2 receptor saturation
- Archive serum

- Chest x-ray
- Abdominal ultrasound and Doppler
- Thyroid ultrasound (at screening and 52 weeks after final transplant)
- Nuclear renal scan if 24-hour urine corrected creatinine clearance is < 80 mL/min/1.73m² and/or serum creatinine is < 1.2 mg/dL on repeated measurement
- Primary care screening referrals:
 - Women:
 - Mammography annually from age 40
 - Pap test according to current American Cancer Association guidelines
 - Men:

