6.6.8 Schedule of Evaluation for UIC Islet Transplant

Visit	A ¹	A ²	A ^{3A}	A ^{3B}	Tx	1	2	3	4	5	6	7	8	9	10	11	12	13	14	15	16	17	18	
Week post transplant	0					1	2	3	4-5	6-7	8-9	10-11	12	16	20	24	28	32	36	40	44	48	52	
History, physical exam	X			X	X	3	3	2	2	2	2	2	X	X	X	X	X	X	X	X	X	X	X	X
Vital signs, weight	X	X	X	X	X	X	X	X	X	X	X	X	X	X	X	X	X	X	X	X	X	X	X	X
Body mass index	X				X				X				X				X							X
BS-SM 7/day	X	X	X	X	X	X	X																	
BS-SM 4/day								X	X	X	X	X	X											
BS-SM 2/day														X	X	X	X	X	X	X	X	X	X	X
CBC	X			X	X	3	3	2	2	2	2	2	X	X	X	X	X	X	X	X	X	X	X	X
CMP, direct bilirubin	X		X	X	X	3	3	2	2	2	2	2	X	X	X	X	X	X	X	X	X	X	X	X
Magnesium					X																			
Phosphorous					X																			
Amylase					X																			
Sirolimus trough level					X	3	3	2	2	2	2	2	X	X	X	X	X	X	X	X	X	X	X	X
Tacrolimus (FK506) trough level					X	3	3	2	2	2	2	2	X	X	X	X	X	X	X	X	X	X	X	X
Alternative immunosuppressant**					X	3	3	2	2	2	2	2	X	X	X	X	X	X	X	X	X	X	X	X
CMV q PCR							X	X	X	X	X	X	X	X	X	X	X	X	X	X	X	X	X	X
EBV q PCR									X		X		X		X		X		X		X		X	
Lipid panel	X			X					X		X		X					X						X
Basal C-peptide	X					3	3	2	2	2	2	2	X	X	X	X	X	X	X	X	X	X	X	X
HbA1c	X		X	X	X					X			X			X			X				X	X
Fructosamine		X			X					X			X			X			X				X	X
Detailed lipid panel		X																						X
Inflammatory panel		X																						X
Antibodies	X												X			X								X
IL2 receptor saturation									X		X		X	X	X	X	X	X	X	X	X	X	X	X
BNP		X			X										X									X
HCG pregnancy (serum)	X			X	X										X									X
Archive research serum		X			X										X									X
Blood type (ABO) (2)	X	X																						
Type, crossmatch					X*																			
PT, PTT, INR	X			X	X																			
QuantIFERON® TB Gold test	X																							
HIV antibody	X			X																				
RPR	X			X																				
Hepatitis panel	X			X																				
EBV panel		X		X*	X*																			
CMV IgG, IgM		X		X*	X*																			
VZV IgG		X		X*																				
PRA	X		X	X		X							X			X			X				X	
Autologous cross match	X																							

Visit	A ¹	A ²	A ^{3A}	A ^{3B}	Tx	1	2	3	4	5	6	7	8	9	10	11	12	13	14	15	16	17	18
Week post transplant	0					1	2	3	4-5	6-7	8-9	10-11	12	16	20	24	28	32	36	40	44	48	52
HLA		X																					
Donor crossmatch					X																		
Urinalysis		X	X		X								X			X							X
24-hour urine creatinine clearance	X																						
Urine culture, sensitivity					#																		

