M/C ratio (random)		X	X	X						X					X					X			X
Sputum culture, sensitivity					#																		
Blood culture, sensitivity					#																		
Glucagon stimulation test	X									X						X							X
Mixed meal test		X														X							X
OGTT										X						X							X
IVGTT										X						X							X
ECG	X			X											X								X
Chest x-ray		X																					X
Abdominal ultrasound, Doppler		X				X																	
Cardiology Consult		X																					
CGMS		X																					X
Primary care	X																						X
Thyroid Ultrasound		X																					X

Visit A: screenings for inclusion

Visits 1 and 2 include 3 evaluations per week; Visit 3 includes 2 evaluations per week; Visits 4 to 7 include 2 evaluations per 2 week period (1 visit per week)

Vital signs: blood pressure, heart rate, respirations, temperature

CMP: comprehensive metabolic profile

CBC: complete blood count

BNP: B-type natriuretic peptide

Antibodies: anti-GAD 65, anti-IA2, anti-islet cell, anti-insulin

IL2 receptor saturation at investigator's discretion

PRA: panel reactive antibodies

Only if hospitalized within the past week

* Only if negative at Screening II

CGMS: continuous glucose monitoring system at Screening A², 1 year after first transplant, 1 year after final transplant

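### Section 6.6.7 joins the two nuclear renal scan conditions with *and/or* where exclusion 14 requires both: a minor error in a procedure rule

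*Protocol*

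**What the plan says.** Protocol Section 6.4.2, exclusion 14, first excludes candidates whose 24-hour creatinine clearance is below 80 mL/min/1.73 m². It then adds: "If corrected creatinine clearance is < 80 and serum creatinine is < 1.2 mg/dL, then a nuclear renal scan is required". The purpose given is to determine GFR.

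Protocol Section 6.6.7 lists examinations to be done according to the Schedule of Evaluation in Section 6.6.8 and the Detailed Visit Schedule appendix. One bullet is the nuclear renal scan. It is triggered by 24-hour corrected clearance below 80 "and/or serum creatinine is < 1.2 mg/dL on repeated measurement".

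In the Section 6.6.8 table, 24-hour urine creatinine clearance is marked once, at screening visit A1. The row "CMP, direct bilirubin", which carries serum creatinine, is marked at every post-transplant visit. There is no row for the scan. SAP Section 17.1.1 reproduces the same table, and the scan does not appear in the protocol's 5-year or 10-year examination lists.

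**The concern.** Two rules in one protocol name the same test and the same two thresholds but combine them differently. Under exclusion 14 a creatinine below 1.2 mg/dL matters only alongside a low clearance. Under Section 6.6.7 as written it can act alone.

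That is also the wrong direction for a creatinine limit standing by itself. Elsewhere such limits are upper limits: exclusion 15 reads "Serum creatinine consistently > 1.5 mg/dL", and SAP Section 10.3 flags creatinine above 1.5 times the upper limit of normal.

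What is at stake is conduct. Followed to the letter, the bullet calls for a nuclear procedure in patients for whom exclusion 14 sees no need of one. Read sensibly as *and*, it leaves staff departing from the written text, and Section 6.12.2 has the monitor check adherence to the protocol.

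**Working it through.** The plan gives no figure to reproduce. The check sets the two triggers side by side.

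**Inputs.** Exclusion 14 (Section 6.4.2): scan if clearance < 80 AND creatinine < 1.2. Section 6.6.7, read literally: scan if clearance < 80 OR creatinine < 1.2, or both. The words about repeated measurement are taken as met.

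| Clearance | Creatinine (mg/dL) | Exclusion 14 | Section 6.6.7, literal |
|---|---|---|---|
| < 80 | < 1.2 | scan | scan |
| ≥ 80 | < 1.2 | no scan | scan |
| < 80 | ≥ 1.2 | no scan (excluded) | scan |
| ≥ 80 | ≥ 1.2 | no scan | no scan |

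The rules disagree in 2 of 4 rows. The two disagreements differ in kind.

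- **Row 2** is the plain error. Exclusion 14 states why the scan is done: "then a nuclear renal scan is required to determine glomerular filtration rate". It uses the scan when a low clearance sits beside an unremarkable creatinine. In row 2 the clearance is not low, so there is no such discrepancy to settle.
- **Row 3** is less clear. At screening no scan is needed because the candidate is already excluded. After transplant a scan in such a patient could be clinically reasonable.

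**Is row 2 unusual?** No. Section 4.2 requires normal kidney function, and exclusion 14 removes clearance below 80 subject to its scan provision. Section 9.1.2 gives mean creatinine in an earlier islet-recipient series: 89 µmol/L before and 104 after transplant, or 79 and 85 without two patients who had abnormal kidney function. Dividing by 88.4 to convert to mg/dL:

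- 89 / 88.4 = 1.01 and 104 / 88.4 = 1.18
- 79 / 88.4 = 0.89 and 85 / 88.4 = 0.96

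All four are below 1.2. These are means from another centre, so they show only that such a value is ordinary in this kind of patient. They do not give a scan count for this trial.

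**When would the bullet operate?** Its clearance limb needs a 24-hour collection, which is scheduled only at A1. The Section 6.6.7 list also contains other screening items, such as the two blood-type tests and the screening thyroid ultrasound. The bullet most likely restates the screening rule.

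**Check of the fix.** With *and* in Section 6.6.7, the last column becomes scan, no scan, no scan, no scan. All four rows then agree with exclusion 14.

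**The case against.** The strongest reply is that the bullet does not stand alone. Its list is to be carried out according to the schedule, the schedule has no scan row, and the Detailed Visit Schedule appendix, whose content is not in the documents at hand, may set timing or trigger. This stands as a limit on consequence. It does not reconcile the two wordings.

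This also disposes of a stronger reading. Because creatinine is drawn at every post-transplant visit, a reader might infer that the bullet orders many scans after transplant. The documents do not support that: the frequency of creatinine draws does not measure how often a rule fires that probably belongs to screening. A reader might likewise infer that renal safety results are compromised. They are not, because the GFR endpoint in protocol Section 6.10.1 and SAP Section 10.1.5 is a Cockcroft-Gault estimate from serum creatinine and does not use the scan.

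Second, an eligibility rule and a monitoring rule need not match. That is fair for row 3 and has no force for row 2.

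Third, the slip might lie in the inequality: if the bullet was meant to say above 1.2, *and/or* would make sense. This cannot be ruled out, but it has little support. Both places print the same sign, and the pairing in exclusion 14 has a clear purpose.

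**Conclusion.** The point holds as a minor error in a procedure rule: the bullet in Section 6.6.7 is wrong as written, and nothing visible in the protocol or SAP reconciles it with exclusion 14. Its extent is 2 of 4 combinations, of which one, clearance of 80 or more with a repeated creatinine below 1.2, is a scan that exclusion 14 gives no reason for. No number of unneeded scans can be derived, and staff may well read the bullet as intended.

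Severity is the lowest level. The primary endpoint, sample size and analysis are untouched. The conclusion assumes that the bullet is meant to carry the same rule as exclusion 14, which the shared test, cut-offs and screening-only clearance make likely but do not prove.

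**What to change.** In the Section 6.6.7 bullet, replace *and/or* with *and*. This is one word, with no change to endpoints, schedule tables, sample size or analysis.

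The cost is row 3: a patient with, for example, clearance 70 and creatinine 1.3 no longer triggers a scan under Section 6.6.7. At screening nothing is lost, since exclusion 14 already excludes that patient. After transplant, a scan can still be ordered under the general provision in Section 6.6.7: "Additional evaluations may be required for medical conditions presenting during the study period and according to best medical practice". The change does not decide whether the scan is meant to apply after transplant at all; the sponsor should say so if it is.

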6.6.8 Schedule of Evaluation for UIC Islet Transplant

Visit	A ¹	A ²	A ^{3A}	A ^{3B}	Tx	1	2	3	4	5	6	7	8	9	10	11	12	13	14	15	16	17	18	
Week post transplant	0					1	2	3	4-5	6-7	8-9	10-11	12	16	20	24	28	32	36	40	44	48	52	
History, physical exam	X			X	X	3	3	2	2	2	2	2	X	X	X	X	X	X	X	X	X	X	X	X
Vital signs, weight	X	X	X	X	X	X	X	X	X	X	X	X	X	X	X	X	X	X	X	X	X	X	X	X
Body mass index	X				X				X				X				X							X
BS-SM 7/day	X	X	X	X	X	X	X																	
BS-SM 4/day								X	X	X	X	X	X											
BS-SM 2/day														X	X	X	X	X	X	X	X	X	X	X
CBC	X			X	X	3	3	2	2	2	2	2	X	X	X	X	X	X	X	X	X	X	X	X
CMP, direct bilirubin	X		X	X	X	3	3	2	2	2	2	2	X	X	X	X	X	X	X	X	X	X	X	X
Magnesium					X																			
Phosphorous					X																			
Amylase					X																			
Sirolimus trough level					X	3	3	2	2	2	2	2	X	X	X	X	X	X	X	X	X	X	X	X
Tacrolimus (FK506) trough level					X	3	3	2	2	2	2	2	X	X	X	X	X	X	X	X	X	X	X	X
Alternative immunosuppressant**					X	3	3	2	2	2	2	2	X	X	X	X	X	X	X	X	X	X	X	X
CMV q PCR							X	X	X	X	X	X	X	X	X	X	X	X	X	X	X	X	X	X
EBV q PCR									X		X		X		X		X		X		X		X	
Lipid panel	X			X					X		X		X					X						X
Basal C-peptide	X					3	3	2	2	2	2	2	X	X	X	X	X	X	X	X	X	X	X	X
HbA1c	X		X	X	X					X			X			X			X				X	X
Fructosamine		X			X					X			X			X			X				X	X
Detailed lipid panel		X																						X
Inflammatory panel		X																						X
Antibodies	X												X			X								X
IL2 receptor saturation									X		X		X	X	X	X	X	X	X	X	X	X	X	X
BNP		X			X										X									X
HCG pregnancy (serum)	X			X	X										X									X
Archive research serum		X			X										X									X
Blood type (ABO) (2)	X	X																						
Type, crossmatch					X*																			
PT, PTT, INR	X			X	X																			
QuantIFERON® TB Gold test	X																							
HIV antibody	X			X																				
RPR	X			X																				
Hepatitis panel	X			X																				
EBV panel		X		X*	X*																			
CMV IgG, IgM		X		X*	X*																			
VZV IgG		X		X*																				
PRA	X		X	X		X							X			X			X				X	
Autologous cross match	X																							

Visit	A ¹	A ²	A ^{3A}	A ^{3B}	Tx	1	2	3	4	5	6	7	8	9	10	11	12	13	14	15	16	17	18
Week post transplant	0					1	2	3	4-5	6-7	8-9	10-11	12	16	20	24	28	32	36	40	44	48	52
HLA		X																					
Donor crossmatch					X																		
Urinalysis		X	X		X								X			X							X
24-hour urine creatinine clearance	X																						
Urine culture, sensitivity					#																		
M/C ratio (random)		X	X	X						X					X					X			X
Sputum culture, sensitivity					#																		
Blood culture, sensitivity					#																		
Glucagon stimulation test	X									X						X							X
Mixed meal test		X														X							X
OGTT										X						X							X
IVGTT										X						X							X
ECG	X			X											X								X
Chest x-ray		X																					X
Abdominal ultrasound, Doppler		X				X																	
Cardiology Consult		X																					
CGMS		X																					X
Primary care	X																						X
Thyroid Ultrasound		X																					X

Visit A: screenings for inclusion

Visits 1 and 2 include 3 evaluations per week; Visit 3 includes 2 evaluations per week; Visits 4 to 7 include 2 evaluations per 2 week period (1 visit per week)

Vital signs: blood pressure, heart rate, respirations, temperature

CMP: comprehensive metabolic profile

CBC: complete blood count

BNP: B-type natriuretic peptide

Antibodies: anti-GAD 65, anti-IA2, anti-islet cell, anti-insulin

IL2 receptor saturation at investigator's discretion

PRA: panel reactive antibodies

Only if hospitalized within the past week

* Only if negative at Screening II

CGMS: continuous glucose monitoring system at Screening A², 1 year after first transplant, 1 year after final transplant

